13.2 Randomization and Stratification

Randomization will be in a ratio of 1:2 in Placebo (4 tablets): erlotinib (4 tablets) by mouth once weekly, based on a permuted block of size 3 with stratification by planned use of agents that significantly decrease Erlotinib bioavailability (tobacco, protein pump inhibitors) and by planned surgery (TURBT vs. cystectomy). The decision was made not to stratify by site to avoid problems with sparse data. After random permutation of numbers from 1 to 3 in each block, incoming subjects in sequence will be randomized to treatment corresponding to the permuted numbers in sequence according to the following: placebo for number 1, and erlotinib for numbers 2 and 3. This process will be repeated after every 3 subjects.

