6.8 Registration/Randomization

Participants will be considered registered on the trial when they sign the consent form. All patients who sign a consent form will be assigned a Participant Identification (PID) number. A set of unique sequential PID numbers will be provided to the PO in the form of a Study Registration Log. This log will be provided to the PO by the CLO at the study initiation.

Randomization

Participants will be randomized according to the scheme outlined in section 3. The study statisticians will provide the CLO with a stratified list of randomization numbers. The DCP Drug repository will also be provided with the list along with the treatment assignment that corresponds to each randomization number.

When an eligible participant is identified at the screening/baseline visit, the site will request randomization of the participant by faxing the appropriate documentation as outlined in the Study Visit Guides to the CLO at [contact].

The CLO will verify eligibility and confirm that the correct version of the informed consent was signed. Once this information is verified, the CLO will assign the next available randomization number from the stratification that applies to the participant (TURBT vs. cystectomy and use of agents which significantly decrease erlotinib bioavailability). The CLO will then fax an Investigational Agent Request form to the DCP drug repository requesting that the bottle of study agent corresponding to the randomization number

assigned the participant be shipped to the site's (investigational) pharmacy by overnight delivery. The site will follow local procedures to have the study agent dispensed to the participant once it is received at the pharmacy.

For next day delivery of study agent, the request for randomization must be received at the CLO office by 2:30 PM Eastern Time (1:30 PM Central Time) on the business day before the drug is needed. Per NCI policy, drug cannot be shipped on a Friday or the day before a holiday. There may be instances where a five-day turn-around is needed (holidays or unusual circumstances). If possible, please randomize a week before the drug is needed.

As soon as a subject has been randomized, the CLO will email a confirmation of randomization to the study coordinator at the PO. If a confirmation is not received within two hours, the coordinator should contact the CLO to confirm that randomization documents were received.

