7.4 Evaluation at Completion of Study Intervention

At the end of study participation, the participant will have research blood work and evaluations for toxicity. The results of these analyses will be compared to the baseline results. At the end of study intervention the following procedures must be completed. The end of study visit has some critical timing requirements to allow for accurate pharmacokinetic measurements in the blood. The final dose of study drug should be taken on the day before surgery on an empty stomach. The participant should be instructed to take this final dose in the evening prior to the day of their surgery. The end-of-study pharmacokinetic blood work must happen approximately 9-18 hours after the last dose of study drug was taken. Please document the date and hour: minute of the last study dose along with the date and hour: minute of the pharmacokinetic blood draw.

Laboratory analyses for safety: **WBC, platelets, hemoglobin, Hct, BUN, total bilirubin, AST, ALT, alkaline phosphatase, creatinine, sodium, potassium, chloride and bicarbonate.**

The participant's **vital signs**, including weight, blood pressure, pulse rate, respiration rate and temperature will be taken.

A review of **concomitant medications** focusing on any changes to the medication list since study initiation and any new medications started since study initiation. Participants should be questioned about medications that have been discontinued prior to surgery.

The coordinator should collect and calculate study **drug compliance**.

International Prostate Symptom Score (I-PSS) – would be completed prior to surgery and the coordinator would collect this.

The participant and coordinator should review any **adverse events** that took place during study participation. The coordinator should record the relevant details about the adverse events as outlined in protocol section 11.

To insure consistency in pharmacokinetic evaluations, all participants should have their end-of-study pharmacokinetic blood work and biomarkers within approximately 9-18 hours after the final dose of study medication. See section 10.2.2 for instructions on drawing and processing the end-of-study pharmacokinetics and biomarkers. Record the date and time of the pharmacokinetic blood draw and the date and time of the last dose of study drug.

Interventions at Time of Surgery

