12. STUDY MONITORING

12.1 Data Management

All of the procedures outlined in the University of Wisconsin Chemoprevention Consortium standardized Data Management Plan (DMP approval 6/3/2013) will be followed in this protocol. There are no supplementary Data Management procedures for this protocol.

This study will report clinical data using the CLO database OnCore which is a web-based clinical trials/database. OnCore will be the database of record for the protocol and subject to NCI and FDA audit. All OnCore data entry will be performed at the CLO where staff is trained in OnCore per our DMP and applicable regulatory requirements such as 21 CFR; Part 11.

In order to standardize the collection of information, the CLO will provide POs with preprinted study-specific source documents.

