13.3 Sample Size and Feasibility

The sample size for each group is based on comparing EGFR phosphorylation in bladder epithelium as measured by quantitative Vectra assay analysis of expression between the erlotinib and placebo arms. This primary endpoint can be considered a continuous random variable. The sample size justification is thus based on a two-tailed two-sample t-test of the difference between the two groups at a significance level of 0.05. In order to detect an effect size of 1, i.e. the difference in the mean change between the placebo arm and the erlotinib arm of 1 standard deviation, with power 0.85, the trial requires an effective sample size of 14 in the placebo arm and 28 in the erlotinib arm. Assuming a random drop-out of up to 5%, 15 subjects in the placebo arm and 30 subjects in the erlotinib arm will be enrolled for a total of 45 subjects for this exploratory study.

There will be six sites participating in the study. Each randomized patient will be treated with study medication weekly x 3 doses. We will allow for study duration of approximately 3 years.

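### Fixed blocks of 3, stated in the protocol, give a lead organization that is meant to stay blind an avoidable means of inferring assignments

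*Combined protocol and SAP*

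**What the plan says.** Section 13.2 describes randomization "based on a permuted block of size 3 with stratification by planned use of agents" affecting bioavailability and by planned surgery, which makes 2 × 2 = 4 strata. Within a block the allocation is "placebo for number 1, and erlotinib for numbers 2 and 3", and "This process will be repeated after every 3 subjects". No variation in block size is described. Site is not a stratification factor: "The decision was made not to stratify by site to avoid problems with sparse data". Section 13.3 adds that "There will be six sites participating in the study".

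Under section 6.8 the CLO checks eligibility and consent, after which "the CLO will assign the next available randomization number from the stratification that applies to the participant". The same section gives the CLO a stratified list of randomization numbers. Only the drug repository's copy is described as carrying the matching treatments.

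Section 12.1 states that "All OnCore data entry will be performed at the CLO". Section 6.9 limits planned unblinding to the study statisticians and repository staff, keeps care and assay staff blinded, and sends each completed unblinding form to the CLO. At the surgery visit (section 7.4), adverse events are reviewed with the participant: "The coordinator should record the relevant details about the adverse events as outlined in protocol section 11".

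**The concern.** At 1:2, three is the smallest possible block and therefore the most predictable. Anyone who knows the block size and the order of entry within a stratum can turn partial knowledge of a block into full knowledge of it. Central assignment keeps that order away from the sites, but it brings order, eligibility checking, adverse event data and any revealed arm together in one office. The plan does not separate these tasks.

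Two things are at stake. The first is concealment: the office that verifies eligibility could sometimes foresee the next arm. The second is tolerance against placebo, the first-prioritized secondary objective. Section 13.5 analyses it partly through the investigator's judgment of relatedness, and section 11.2.2 has the lead organization as well as the sites report serious events, including attribution to drug.

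**Working it through.** **The plan's own figure.** The plan gives no measure of predictability. Its sample size reproduces: placebo n = (1 + 1/2)(1.960 + 1.036)² / 1² = 13.5, so 14, with 28 on erlotinib. Dividing by 0.95 gives 15 + 30 = 45. Exact t-test power at 14/28 is 0.846. Block size does not enter this calculation.

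**What one block reveals (one placebo, two erlotinib).**
- One placebo revealed: both others are erlotinib with certainty.
- One erlotinib revealed: each other member moves from 0.667 to 0.50 erlotinib, and nothing is settled.
- Two erlotinib revealed: the third is placebo with certainty.

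Unblinding one participant at random therefore settles two others with probability 1/3 and none with probability 2/3.

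**Worst case: all earlier assignments in the stratum known.**
- Certainty by position: the first is never certain, the second is certain if the first was placebo (1/3), and the third is always certain. Mean = (0 + 1/3 + 1)/3 = 4/9 = 44.4%.
- Best-guess accuracy by position is 2/3, 2/3 and 1. Mean = 7/9 = 77.8%.
- Mixed blocks, each 3 or 6 with probability 1/2 and both sizes known to the observer, calculated exactly: 8.9% certain with 12 participants in a stratum (8.1% with 9, 9.1% with 15). Best-guess accuracy is 75.0%.

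**Inference from rash alone.** Let p be the rash rate on erlotinib and q the rate on placebo. Neither is given for 600 mg weekly, so both are assumptions. For p, 0.75 is the daily 150 mg bladder trial (section 6.2) and 0.917 is 11/12 at 1200 to 2000 mg weekly (section 2.2). The values 0.25 and 0.50 extend the range downward.

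If q = 0, the next assignment is certain only when it is third in its block (1/3), the placebo falls there (1/3) and both earlier members had rash (p²), which gives p²/9. After the fact, a block's placebo is settled when both erlotinib members had rash, which gives 15p² of the 15 placebo assignments.

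| p | Next assignment certain, q = 0 | Placebo settled of 15, q = 0 | Best guess without / with block knowledge, q = 0 | Same, q = 0.1 |
|---|---|---|---|---|
| 0.25 | 0.7% | 0.9 | 66.7% / 68.7% | 66.7% / 67.3% |
| 0.50 | 2.8% | 3.8 | 66.7% / 75.0% | 66.7% / 72.5% |
| 0.75 | 6.25% | 8.4 | 83.3% / 85.4% | 80.0% / 82.3% |
| 0.917 | 9.3% | 12.6 | 94.4% / 94.7% | 91.1% / 91.4% |

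With q above 0, no assignment is certain from rash alone. Over p from 0.25 to 0.917 and q from 0 to 0.2, block knowledge adds 0 to about 8 percentage points to a best guess based on rash.

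**The case against.** The strongest reply is that the 44% assumes knowledge the design withholds. The CLO's list is not described as showing treatments, so it would have to build up knowledge from rashes and occasional unblindings. On that route the share of next assignments that are certain is single-digit percent at best. Rash itself is the main unblinder, and no block size changes that. Blocks of 3 also hold the 1:2 ratio closely when 45 participants are spread over four strata. All of this stands, and it limits the size of the point.

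Two stronger readings are tempting. A reader might infer that one rash or one unblinding exposes many assignments. It does not: a rash points to erlotinib, and one known erlotinib recipient settles no block mate. Many follow only if rash is both frequent and specific to erlotinib, which the documents do not establish at this dose.

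A reader might also infer that the tolerance comparison is undermined. The documents do not show that. Site staff examine participants and record events, grading follows CTCAE version 4.0, and sites are not described as holding the stratum sequence, which runs across six sites. The CLO's described role for most events is data entry, with serious event reporting as the exception. Whether CLO staff also work at a clinical site is not stated.

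Nor do the documents say that the block size was public during enrolment, only that the protocol states it.

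What the reply does not remove is the combination of tasks at an organization that is meant to stay blind, and its ability to foresee some assignments while verifying eligibility.

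**Conclusion.** The point holds as an avoidable, minor risk. The block is fixed, of minimum size and written in the protocol, and central assignment relocates the predictability without removing it. The certain share falls from 44% to about 9% under mixed blocks, but this is a worst case that assumes all earlier assignments are known, and the matching gain in best-guess accuracy is about 3 points. Inference from rash alone gives much less: p²/9 of next assignments if placebo never produces rash, and none with certainty otherwise. The rash rates are assumptions borrowed from other doses and schedules.

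Allocation concealment carries most of the risk. The judged tolerance endpoint carries some, mainly where the CLO handles attribution of serious events. The primary endpoint is largely protected, because it is a quantitative tissue measurement made by blinded staff. Sample size and nominal power are unaffected.

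**What to change.** For participants not yet randomized, have the statistician generate randomly mixed blocks of 3 and 6 within the four existing strata. Replace the block description in section 13.2 with a statement that permuted blocks of varying size are used, and hold the sizes in a restricted randomization file. It would also help, where staffing allows, for the CLO to separate the person who assigns numbers from those who enter adverse event data and receive unblinding forms.

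The 1:2 ratio, strata, sample size and nominal power stay as they are. The costs are a protocol amendment with IRB approval (section 14.3), reissue of the number list to the CLO and of the number-to-treatment list to the repository, and slightly larger possible imbalance within strata and overall. In a simulation of 45 participants with assumed stratum shares of 35, 35, 15 and 15%, the standard deviation of the total on placebo rises from about 0.8 to about 0.9. The change does not address unblinding by rash itself.

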13.3 Sample Size and Feasibility

The sample size for each group is based on comparing EGFR phosphorylation in bladder epithelium as measured by quantitative Vectra assay analysis of expression between the erlotinib and placebo arms. This primary endpoint can be considered a continuous random variable. The sample size justification is thus based on a two-tailed two-sample t-test of the difference between the two groups at a significance level of 0.05. In order to detect an effect size of 1, i.e. the difference in the mean change between the placebo arm and the erlotinib arm of 1 standard deviation, with power 0.85, the trial requires an effective sample size of 14 in the placebo arm and 28 in the erlotinib arm. Assuming a random drop-out of up to 5%, 15 subjects in the placebo arm and 30 subjects in the erlotinib arm will be enrolled for a total of 45 subjects for this exploratory study.

There will be six sites participating in the study. Each randomized patient will be treated with study medication weekly x 3 doses. We will allow for study duration of approximately 3 years.

13.4 Primary Objective

The primary objective is to determine if there is a difference in EGFR phosphorylation in normal appearing bladder epithelium adjacent to tumor approximately 9-18 hours post-study dose, between patients randomized to erlotinib weekly as compared to placebo. The primary endpoint of the study is EGFR phosphorylation in bladder epithelium at the end of study (weekly for 3 doses) in subjects with bladder cancer. For the primary comparison the difference between the placebo group and the erlotinib group will be tested as-randomized using a two-sample t-test with normalizing transformation if necessary or Wilcoxon rank-sum test.

Because of the required dose modification to 300 mg for grade 2 rash or diarrhea and allowed dose modification for grade 1 rash/diarrhea if subject prefers (refer to section 5.6) there is the potential for a number of patients to reduce dose at some point in the study. In addition, prior research has shown that smokers and those that regularly take proton pump inhibitors metabolize erlotinib faster, tolerating

erlotinib better, but gaining fewer benefits, effectively receiving a reduced dose compared to non-smokers and those that are not taking proton pump inhibitors (refer to section 2). As a supporting analysis for the primary endpoint we will explore a relationship for EGFR phosphorylation with a measure of dose received, and accounting for smoking status and proton pump inhibitor use.

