2.2 Study Agent

Erlotinib HCl (Tarceva) is an orally available, highly selective, reversible inhibitor of epidermal growth factor receptor (HER1/EGFR) tyrosine kinase. Inhibition of tyrosine kinase activity prevents HER1/EGFR phosphorylation, the associated downstream signaling events, and may block tumorigenesis mediated by inappropriate HER1/EGFR signaling. Erlotinib inhibits the intracellular phosphorylation of tyrosine kinase associated with the EGFR. The recommended dosing in adults is a daily oral dose of 150 mg continuously or until dose-limiting toxicity leads to an interruption and possible reduction in daily dosing.

Erlotinib pharmacokinetic analyses have been characterized by the following observations; a relatively long half-life (10-12 hours), predominant metabolism via P450 metabolism with some correlation to hepatic function, and increasing AUC values with repeated daily dosing (White-Koning 2011, Hamilton 2006). Also multiple studies have correlated an increasing AUC of erlotinib or gefitinib with the occurrence of skin toxicity (White-Koning 2011, Thomas 2009) while there are other studies, which have not confirmed this association (Calvo 2007). Current smokers have been observed to tolerate erlotinib and gefitinib better than non-smokers but also to have less benefit observed. Consistent with these observations Hamilton et al (Hamilton 2006) performed a comparison pharmacokinetic study of erlotinib in current smokers and non-smokers at doses of 150 and 300 mg. They observed that current smokers had AUC and Cmax values approximately half of non-smokers or smokers at 300 mg had AUC values similar to non-smokers at 150 mg daily. It is theorized the likely explanation of this is the known contribution of CYP1A1 and CYP1A2 to the metabolism of erlotinib and their induction by cigarette smoking.

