13.6 Reporting and Exclusions

As the nature of this study is exploratory, intent-to-treat should not be used as a principal analysis criteria. Nevertheless, no subjects will be excluded from the analysis and reporting, except for obvious random dropouts and for those who never took the protocol treatment.

Compliance with the protocol treatment will be measured in the form of pill counts; the information will not be used for the primary analysis, but for the analysis supporting the primary endpoint. There will be no imputation of missing data for both the primary and the secondary endpoints.

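### The supporting analysis in 13.4 relates the endpoint to a dose that is cut for toxicity, so if toxicity tracks exposure its within-erlotinib slope is biased toward zero; surgery-day plasma level should be added as the main exposure measure

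*Combined protocol and SAP*

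**What the plan says.** - **The analysis.** Section 13.4 notes that some participants may have their dose reduced, and that smokers and regular PPI users in effect receive less drug. It therefore plans to "explore a relationship for EGFR phosphorylation with a measure of dose received, and accounting for smoking status and proton pump inhibitor use".
- **The data behind it.** Section 13.6: "Compliance with the protocol treatment will be measured in the form of pill counts". It reserves that information for the supporting analysis and keeps it out of the primary one.
- **How dose comes to vary.** Section 5.6 halves the dose for unacceptable grade 1 rash or diarrhea, grade 2 skin toxicity, grade 2 diarrhea unresponsive to loperamide, any event of grade 3 or above, or at physician discretion.
- **Toxicity and exposure.** Section 2.2: "multiple studies have correlated an increasing AUC of erlotinib or gefitinib with the occurrence of skin toxicity". The same sentence adds that other studies did not confirm the association. Sections 8.2 and 9.1 justify the pharmacokinetic work by this link, and 9.1 calls it consistent.
- **Plasma level.** Section 7.4: "end-of-study pharmacokinetic blood work must happen approximately 9-18 hours after the last dose of study drug". Dose and draw times are recorded to the minute. The draw is scheduled for every participant at surgery (7.1), and erlotinib and OSI-420 are assayed (9.1). The stated uses are descriptive pharmacokinetics (13.5) and a compliance check (5.7.2). No planned analysis relates plasma level to EGFR phosphorylation.

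**The concern.** Within the erlotinib arm, dose received is not an assigned level. It is partly a consequence of how the participant responded to earlier doses. If high exposure causes the toxicity that triggers the cut, the lower recorded doses belong disproportionately to participants with high exposure per tablet. That is confounding by indication, and it works against finding a dose relationship.

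Section 8.1 gives the primary goal as judging whether tissue delivery and duration of effect are enough to justify further testing. If the primary comparison is weak, the team will want to separate too little drug from no drug effect. The 13.4 analysis is the only planned tool for that, and it uses the more vulnerable exposure measure although a more direct one has been collected.

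**Working it through.** **1. The plan's own figure.** Section 13.3 uses a "two-tailed two-sample t-test of the difference between the two groups at a significance level of 0.05", with 1:2 allocation and a difference of 1 SD, and says "with power 0.85, the trial requires an effective sample size of 14 in the placebo arm and 28 in the erlotinib arm".
- Placebo n = (1 + 1/2)(1.96 + 1.036)² = 13.5, so 14, and erlotinib 28.
- Power at 14/28: √(14 × 28/42) = 3.055, and 3.055 - 1.96 = 1.095, giving 86.3% by the normal approximation and 84.6% by the noncentral t.
- Dropout of 5%: 14/0.95 = 14.7 and 28/0.95 = 29.5, so 15 + 30 = 45.

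The figure reproduces. The plan gives none for the supporting analysis.

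**2. Direction of the bias.** Suppose the effect is proportional to exposure. Let F and R be the mean exposure that a full dose would give in participants kept on full dose and in those reduced.
- 50% cut: slope per full-dose unit = (-F + 0.5R)/0.5 = -(2F - R). If R = F this is the true slope. If R > F it shrinks relative to F. It reaches zero at R = 2F.
- 25% cut (the three-tablet reading of 7.3): slope = (-F + 0.75R)/0.25 = -(4F - 3R), which reaches zero at R = 4F/3.

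**3. Size, by simulation** (up to 3,000 trials per scenario).
- From the documents: 28 erlotinib and 14 placebo participants; exposure halved in smokers or PPI users (2.2 reports about half for smokers, 5.5 reports -46% for omeprazole); a 50% cut.
- Assumed, not in the documents: half the participants are smokers or PPI users; 35% are reduced; residual SD of log exposure 0.3-0.7; log-odds of reduction rise by γ = 0 to 3 per unit of log exposure; true effect -1 SD at mean full-dose exposure, linear in last-dose exposure; log-SD error of 0.25 on the plasma level.

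Mean slope (power); true slope -1.0; the dose columns are adjusted for smoking/PPI:

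| SD, γ | Dose, erlotinib only | Plasma, erlotinib only | Dose, with placebo |
|---|---|---|---|
| 0.5, 0 | -0.98 (17%) | -0.84 (70%) | -0.99 (69%) |
| 0.5, 1 | -0.71 (11%) | -0.83 (61%) | -0.90 (62%) |
| 0.5, 2 (mid case) | -0.42 (7%) | -0.79 (46%) | -0.81 (54%) |
| 0.5, 3 | -0.19 (4%) | -0.75 (36%) | -0.74 (47%) |
| 0.7, 1 | -0.40 (5%) | -0.86 (71%) | -0.81 (50%) |
| 0.7, 2 | +0.05 (2%) | -0.82 (58%) | -0.69 (39%) |
| 0.7, 3 | +0.27 (2%) | -0.82 (51%) | -0.63 (34%) |

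- Over all scenarios with γ = 1-3, the erlotinib-only dose slope runs from -0.92 to +0.27 (power 2-17%) and the plasma slope from -0.69 to -0.86 (27-71%). With placebo, dose gives -0.94 to -0.63 (34-68%) and plasma -0.85 to -0.90 (73-89%).
- In the mid case, smoking/PPI adjustment moves the dose slope from -0.17 to -0.42: a real but partial correction.
- With 15% or 50% reduced, the adjusted mid case is -0.49 or -0.38. With a three-tablet reduced dose it is +0.45 in the erlotinib arm and -0.89 with placebo.

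**4. Limit of one plasma level.** With the 10-12 h half-life in 2.2, the level falls by a factor of 2^(9/12) = 1.7 to 2^(9/10) = 1.9 between 9 and 18 h, so recorded time since dose belongs in the model.

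**The case against.** The case for leaving the plan alone has real parts.

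- **Smoking and PPI use are already in the model.** This stands in part: adjustment removes some of the bias. Other differences in clearance remain, and only the plasma level captures them.
- **The exposure-toxicity link is mixed evidence.** This stands. With γ = 0 the dose slope is unbiased (-0.98 to -1.02). Some cuts under 5.6 also need not track exposure, such as those for participant preference or an unrelated grade 3 event. Missed tablets and the fourth dose after delayed surgery (5.2) add further variation of that kind.
- **Placebo is not excluded.** Section 13.4 does not restrict the analysis to erlotinib, and 13.6 argues against exclusions. With placebo at zero dose the slope never reverses in these scenarios. Much of that slope, however, is the between-arm contrast that the primary test already makes.
- **Low power is not mainly confounding.** In the mid case power falls from 17% with no link to 7%; the 17% ceiling comes from few reductions and 28 participants.
- **The simulation favours plasma.** The response was generated from exposure, and the plasma regression used the level itself without the smoking/PPI stratum. In a separate simulation, log plasma level adjusted for the stratum and measured without error was significant in only about 14-36% of trials. Plasma level is also not randomized.
- **The analysis is exploratory.** No decision rule uses it.

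A reader might infer that the planned analysis is bound to show no relationship or a reversed one. The documents do not support that: it needs a strong link and high exposure variability (with a 50% cut), and placebo left out. A reader might also infer that dose received should become descriptive only. That would drop a question 13.4 poses itself, namely what dose reductions do to the endpoint.

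**Conclusion.** The point holds as a bias that depends on the exposure-toxicity link. If toxicity rises with exposure, as the protocol's own pharmacokinetic rationale supposes, the within-erlotinib dose slope is pulled toward zero despite the planned adjustment. In the mid case it keeps 42% of the true slope, against 79% for plasma level and 81% for dose with placebo included. With a 50% cut, the adjusted slope passes zero only at the highest variability tried (SD 0.7, γ = 2-3). The direction follows from sections 5.6 and 2.2 and the algebra above; the size rests on assumed exposure variability, reduction rate and strength of link, none of which the documents give.

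The planned analysis is therefore a weak basis for exposure-response statements on its own, and a more direct measure is already in hand. The primary as-randomized comparison and the enrolment of 45 are untouched.

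**What to change.** In 13.4:

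1. Add log plasma erlotinib at the surgery visit, with OSI-420 alongside, as the main exposure measure within the erlotinib arm. Adjust for recorded hours since the last dose, and report with and without the smoking/PPI stratum.
2. Keep the planned dose-received analysis as secondary, state that it is confounded by toxicity-driven reduction, and report it with and without placebo.
3. Describe both as exploratory.

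The cost is SAP wording and slightly more analysis; no new samples or data are needed. The drawback is that a single plasma level is noisy and not randomized.

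Separately, the reduced dose is two tablets in 5.6 (300 mg in 13.1 and 13.4) but three tablets in the Day 8 text of 7.3. These passages must be reconciled, because dose received, and the size of the bias, depend on which applied.
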